Inclusion criteria:	
- Women 18 years or older- Study IIA: patients with early stage cervical cancer with tumour size >2 cm*, FIGO stage IB1, IB2 or IIA1- Study IIB: patients with high risk endometrial cancer, type 1 histology grade 3 Endometrioid adenocarcinoma or type 2 histology (serous-, clearcel-, carcinosarcoma or undifferentiated adenocarcinoma.- Capable of filling out questionnaire in Danish- Booked for robotic assisted operation
Exclusion criteria:	
- Prior PLD- Known allergy towards ICG and/or iodine (ICG contains 5% sodium iodine)- Women included in other studies affecting outcome-measures of the present study- Women where pelvic lymphadenectomy is discarded or previously performed been deselected due to reasons related to the patients health status- Women in active treatment for a secondary cancer diagnosis within the past 5 years (excl. basal cell carcinoma)- Women with dementia

total hysterectomy, PLD and PALD are eligible.

*The size of the cervical tumour will be determined by clinical evaluation in the diagnostic gynaecologic examination as customary.

Both studies will be commenced at Odense University Hospital, Copenhagen University Hospital from March 2017 and at Aarhus University Hospital from June 2018. International collaboration will be sought to assist in inclusion due to the low number of eligible patients in Denmark. Patients will be included over a three-year period from February 2017 to February 2020. A total of 100 patients in Study IIA and 150 patients in Study IIB (please see the power calculation) will be included in this two-year inclusion period. The study period may be extended until the expected number of patients are included.

Study design

Both studies are prospective observational diagnostic studies with the purpose of investigating the diagnostic safety of SLN mapping and FDG-PET/CT to detect lymph node metastases. All patients will receive SLN mapping and removal of FDG-PET/CT positive lymph nodes followed by conventional radical PLD and for endometrial cancer also PALD.

Please see appendix 3-4 for flowcharts of the procedure.

FDG-PET/CT scans will be performed in all patients prior to surgery. An experienced specialist in nuclear medicine will systematically describe the FDG-PET/CT for each patient prior to surgery.

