FDG-PET/CT positive lesions are described with exact anatomic localizations (appendix I), size and amount. All lesions will be evaluated on an ordinal scale ranging from 0 to 3. A score of 0 or 1 carry the meaning of 'no' or 'probably no' signs of metastasis, and a score of 2 or 3 carry the meaning of 'probable' or 'definite' signs of metastasis, respectively. For overall accuracy analyses, these values will be dichotomized into test negative (0 and 1) and test positive results (2 and 3). Furthermore, in all FDG avid lesions, the standard uptake value (SUV) will be registered for quantification purposes. Blood sugar levels will be taken on patients in order to calculate the SUV.

Surgical Procedure:

Shortly prior to surgery a vial of 25 mg ICG is diluted with 20 ml of sterile water to produce a 1.25 mg/ml concentration. For each patient, a new vial of ICG is used due to degradation of the fluorescence signal of ICG after dissolving. The same vial of ICG may however be used for several patients if the patients are operated the same day, since degradation of the fluorescence signal of ICG after dissolving is very low within the first 24 hours. When the woman has been anesthetized and immediately prior to surgery, 4 ml of the 1.25mg/ml ICG solution is injected into the cervix.. An injection of 2 ml will be made on each side of the cervix at positions 3 and 9 o'clock, with 1 ml deep in the cervical stroma (>10 mm) and 1 ml submucosally (< 5 mm).

The surgical robot is routinely docked and the NIR fluorescence system is initiated. All standard locations of a PLD are examined for fluorescence using the NIR fluorescence imaging system. Fluorescent hotspots are denominated as SLNs and the amount and localization are described and drawn into an anatomical illustration (Appendix I). All denominated SLNs are then removed surgically and sent for ultra-staging. The FDG-PET/CT positive lymph nodes will be localized following the SLN mapping. If the FDG-PET/CT positive lymph node has already been nominated as a SLN, the lymph node- will be labeled SLN and FDG-PET positive. Any enlarged lymph nodes suspicious of metastatic disease will be removed and marked as such with the predefined anatomical location (Appendix I). Finally radical PLD is performed in all women. Women with endometrial cancer will further undergo PALD to the level of the renal vein.

Pathology:

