The LYMQOL questionnaire will be translated to Danish using independent forward-backward translation and pilot tested before administration.

The questionnaires are completed as paper/pen version or electronically at the patient's individual preference at 3, 12, 24, and 36 months after surgery. The incidence of early lymphedema will be evaluated at 3 months postoperatively as a difference score between 3 months and the baseline score. The course of chronic lymphedema will be evaluated over time. Written reminders will be sent once after three weeks at each questionnaire interval if the patient has not responded.

Sociodemographic variables will be collected using a questionnaire designed for the purpose and included in the first questionnaire package. The sociodemographic variables include Danish social security number, age, hospital, date of inclusion, BMI, smoking status and contact information. Other data recorded from patient medical files include comorbidity, prior abdominal surgery, type of cancer, presumed preoperative FIGO stage, final FIGO stage postoperatively and whether or not the patient undergoes postoperative oncological therapy. This information will be used for stratification and adjustment in the analyses of lymphedema and quality of life.

Special considerations

In Study IIA radiologically and/or clinically suspected lymph nodes may be sent for frozen section to rule out the metastatic disease. Alternatively, a two-step procedure: removal of suspected lymph nodes for histology as a first step operation followed by completion surgery as a second step, if no metastatic disease in the removed lymph nodes is revealed. If metastatic lymph node involvement is histologically confirmed intra-operatively, the surgical procedure of women with cervical cancer will be terminated and the patient will be referred for chemo-radiotherapy.

In study IIB In case of clinically highly suspicious lymph nodes a frozen section evaluation is recommended, and if metastatic disease is identified, systematic PLD and PALD should be abandoned and replaced by removal of all clinically and by imaging suspicious lymph nodes in the pelvic and paraaortic area. All women with serous adenocarcinomas and with carcinosarcomas should further undergo infracolic omentectomy (31).

Primary outcome measurements

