Study IIA: The overall sensitivity of SLN mapping combined with removal of FDG-PET/CT positive lymph nodes in the detection of lymph node metastases. Due to the low prevalence of the disease this study is primarily explorative.

Study IIB: The NPV of SLN mapping combined with FDG-PET/CT. Please see below for a power calculation.

Secondary outcome measurements

Study IIA:

- Prevalence of lymph node metastasis.
- The detection rate of SLNs. The positive- and negative predictive values of SLN mapping per patient and per hemi-pelvis.
- The positive- and negative predictive value, sensitivity and specificity analyses of FDG-PET/CT.
- The specific size of the cervical tumour determined by a combination of MR imaging, pathology and clinical evaluation will be described for comparison.
- Incidence and severity of lymphedema and quality of life assessment of all patients.

Study IIB:

- Prevalence of lymph node metastasis.
- The detection rate of SLNs in high risk endometrial cancer.
- The sensitivity of SLN mapping per patient.
- Incidence and severity of lymphedema and affection of quality of life after SLN mapping, PLD and PALD.
- Intra- and postoperative complications after surgery with SLN mapping, PLD and PALD.

Statistical analysis

Study IIA cervix cancer:

The exact prevalence of lymph node metastases in cervical cancers of > 2cm is not known from the literature. In studies including low risk cervical cancer patients (tumors < 20 mm) it has been estimated to be < 10%. The present study is explorative and will include 100 patients in Study IIA (cervical cancer) who have undergone PLD after SLN mapping.

Further, the rate of true positive (TP), false positive (FP), false negative (FN) and true negative (TN) findings of PET/CT and SN mapping will be identified to assess the positive predictive value,

the negative predictive value, the sensitivity of PET/CT and SN mapping, respectively. Explorative comparisons will be made for each of the intervention tests (PET/CT and SN mapping).

Study IIB endometrial cancer:

Amendment 04.12.2020

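### The 100 and 150 women are counted by completed dissection, but the protocol stops dissection when a node is proven metastatic; taken as the evaluable population, these counts lose node-positive women and bias sensitivity and prevalence

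*Protocol*

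**What the plan says.** **Everyone has the dissection.** Protocol, Study design: "All patients will receive SLN mapping and removal of FDG-PET/CT positive lymph nodes followed by conventional radical PLD", with PALD added in endometrial cancer. Surgical Procedure repeats it: "Finally radical PLD is performed in all women".

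**Not everyone has it.** Under Special considerations, Study IIA, "radiologically and/or clinically suspected lymph nodes may be sent for frozen section to rule out the metastatic disease". If nodal metastasis is confirmed during surgery, the operation ends and the woman goes to chemo-radiotherapy. In the alternative two-step route, the second operation takes place only if the nodes removed first are free of metastasis. For Study IIB, frozen section is recommended for clinically highly suspicious nodes. A metastatic result means that systematic PLD and PALD are abandoned and only suspicious nodes are removed.

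**The counts.** Study population gives the numbers as women included: "A total of 100 patients in Study IIA and 150 patients in Study IIB". Statistical analysis attaches a condition. Study IIA "will include 100 patients in Study IIA (cervical cancer) who have undergone PLD after SLN mapping", and the IIB calculation rests on women with SLN mapping followed by PLD and PALD, of whom 150 are needed.

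**The outcomes.** The IIA primary outcome is the sensitivity of SLN mapping combined with removal of PET/CT-positive nodes. The IIB primary outcome is the NPV of SLN mapping combined with FDG-PET/CT. Prevalence of nodal metastasis is secondary in both studies, PET/CT sensitivity in IIA, and SLN sensitivity in IIB.

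**The concern.** The two groups of statements cannot both hold as written, and the analysis counts use the very condition that Special considerations removes. Its only trigger for stopping is a histologically proven nodal metastasis; women whose suspicious nodes prove negative go on to dissection. So the women whom this rule takes out of a count of completed dissections are all reference-positive.

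Sensitivity and prevalence depend directly on that group. Node-positive women are the whole denominator of the IIA primary outcome, and there will be few of them. Losing true positives lowers the observed sensitivity; losing false negatives raises it. Downward is the likelier direction in IIA, because radiological suspicion is one route to frozen section and overlaps with a positive PET/CT, which would make the woman test-positive. That is an inference, not something the protocol states.

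**Working it through.** **1. The plan's own figure.** IIB assumes 20% metastasis and 96% sensitivity of the SLN algorithm, so true NPV = 0.80 / (0.80 + 0.20 × 0.04) = 99.0%. With 150 women and a one-sided 95% Clopper-Pearson lower bound required to exceed 94%, exact power is 89.3%. The protocol states no target power, so 150 is plausible but cannot be strictly reproduced. The point does not depend on it.

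**2. IIA primary sensitivity.** The protocol gives no number stopped and calls prevalence for tumours above 2 cm unknown. Assumptions: 12, 17 or 22 node-positive of 100 (the 12–22% in Background is for early-stage cervical cancer generally), 2 false negatives, and L women lost. With n node-positive women:
- full set: (n − 2)/n
- all lost are true positives: (n − 2 − L)/(n − L)
- one of those lost is a false negative: (n − 1 − L)/(n − L)

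| n | Full set | L = 1, true positive | L = 3, all true positives | L = 3, one false negative |
|---|---|---|---|---|
| 12 | 10/12 = 83.3% | 9/11 = 81.8% | 7/9 = 77.8% | 8/9 = 88.9% |
| 17 | 15/17 = 88.2% | 14/16 = 87.5% | 12/14 = 85.7% | 13/14 = 92.9% |
| 22 | 20/22 = 90.9% | 19/21 = 90.5% | 17/19 = 89.5% | 18/19 = 94.7% |

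**3. IIA PET/CT sensitivity.** With 17 node-positive women and 3 PET-positive women lost, an assumed 14/17 = 82.4% becomes 11/14 = 78.6%, and an assumed 5/17 = 29.4% becomes 2/14 = 14.3%.

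**4. IIB secondary SLN sensitivity.** Node-positive women: 150 × 20% = 30. With 2 false negatives assumed, 28/30 = 93.3%. Losing 3 gives 25/27 = 92.6% (all true positives) or 26/27 = 96.3% (one false negative).

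**5. Prevalence with 3 lost.** IIA: 17/100 = 17.0% becomes 14/97 = 14.4%. IIB: 30/150 = 20.0% becomes 27/147 = 18.4%.

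**6. IIB primary NPV.** NPV uses only test-negative women, so losing true positives leaves it unchanged. It moves only if a stopped woman was negative on both SLN and PET/CT. The plan implies 30 × 4% = 1.2 false negatives. One-sided 95% lower bounds with 120 true negatives:

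| False negatives | Lower bound |
|---|---|
| 2 | 94.9% |
| 3 | 93.8% |
| 6 | 90.8% |
| 7 | 89.9% |

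Dropping one false negative crosses 94% only from 3 to 2, and 90% only from 7 to 6. With false negatives distributed Binomial(30, 0.04), the chance of 3 or more is 12% and of 7 or more 0.015%. One of them must also be a stopped woman.

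**7. Meaning of the counts.** If a share f of node-positive women is stopped, reaching N completed dissections takes N / (1 − f × prevalence) women. With f = 50% assumed, IIB needs 150 / (1 − 0.5 × 0.20) ≈ 167, and IIA at 17% needs 100 / (1 − 0.5 × 0.17) ≈ 109.

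**The case against.** The strongest reply is that the quoted counts are sample-size statements, not declared analysis sets. The sentence on identifying true and false positives and negatives carries no PLD restriction, and an accuracy set is commonly defined in a SAP, which is not at hand. The IIB calculation also uses a prevalence taken before any stopping, and the same 150 appears as women included. This suggests that the authors overlooked the exception rather than chose to drop anyone. All of that stands. A reader might infer that the protocol excludes stopped women, but it does not say so. What remains is that the protocol itself writes completed dissection into its counts and contradicts itself about who receives it, which is more than missing detail.

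A reader might also infer that the count drops only node-positive women, or that the two versions of 100 and 150 differ by exactly the stopped women. The text does not support that: women may withdraw consent at any time (Recruitment of patients) or miss PLD for other reasons. The one-sidedness applies only to losses caused by Special considerations.

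It can be said, too, that Special considerations is simply an exception to the general procedure, and that SLNs come first in the described sequence ("All denominated SLNs are then removed surgically and sent for ultra-staging"), so a woman stopped late already has an index-test result. That is fair, and it is why she can be scored. It does not settle the two-step route, where the text does not say whether SLN mapping is done at the first operation; the flowcharts in appendices 3–4, which are not shown, may do so.

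Finally, the shifts are small beside the sampling error: the exact 95% interval for 15/17 is 63.6% to 98.5%. That is true, but this is an avoidable bias added to an already imprecise estimate, and more women would not remove it.

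**Conclusion.** The point holds in conditional form and should be fixed. If completed dissection is applied literally as the evaluable population, the losses caused by the stopping rule are all node-positive. They bias the IIA primary sensitivity, the IIA PET/CT sensitivity and the IIB SLN sensitivity, and lower prevalence in both studies.

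The size is unknown. Frozen section is optional in IIA and recommended in IIB, and the numbers stopped, node-positive and false negative used for IIA are assumptions. Over the illustrated range, losing 1 to 3 true positives lowers IIA sensitivity by 0.4 to 5.6 percentage points. Losing 3 women of whom one is a false negative raises it by 3.8 to 5.6 points.

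IIA is explorative without a threshold, so the harm is a biased primary estimate and not a wrong decision. A reader might infer that the IIB conclusion on NPV is also at risk; under the plan's own assumptions it is essentially unaffected.

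**What to change.** 1. Define the per-patient accuracy set as all women with PET/CT and SLN mapping whose nodal status is established either by completed dissection or by histologically proven nodal metastasis.
2. Score stopped women as reference-positive. Score them as test-positive if any SLN (including on ultra-staging) or any PET-positive node was metastatic, and otherwise as false negatives under the test defined in Primary outcome measurements. For this scoring only, say whether removal of enlarged nodes, which Background lists in the SLN algorithm, counts as part of the test; if it does, a woman whose removed enlarged node was metastatic is a true positive.
3. Keep women found metastatic before SLN mapping in prevalence and PET/CT accuracy, and report them separately. Leave stopped women out of per-hemipelvis and node-count analyses only.
4. State whether 100 and 150 mean women included or women with completed dissection.
5. Reconcile Study design and Surgical Procedure with Special considerations. No change to surgical management is proposed.

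The cost is wording plus one data check. For PET/CT, "FDG-PET/CT positive lesions are described with exact anatomic localizations (appendix I), size and amount", and for enlarged nodes, "Any enlarged lymph nodes suspicious of metastatic disease will be removed and marked as such with the predefined anatomical location". However, the Pathology section lists the location of metastases only for SLNs, so the sponsor should confirm that the records link PET status to metastatic non-SLNs.

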Appendix I. Predefined anatomical locations, for registration of lymph nodes.

Højre side:

- A: Paraaortalt
- A1= Under AMI
- A2= Over AMI
- A3= Ved højre nyrevene
- C: Aa. Iliaca Communis
- E: Præsakralt
- G: A. Iliaca Externa
- H: A. Iliaca Interna
- K: Fossa Obturatoria

Venstre side:

- B: Paraaortalt
- B1= Under AMI
- B2= Over AMI
- B3= Ved venstre nyrevene
- D: Aa. Iliaca Communis
- F: Præsakralt
- J: A. Iliaca Externa
- I: A. Iliaca Interna
- L: Fossa Obturatoria

Appendix II. English version of all included PROMs

EORTC IL76

ENGLISH

EORTC IL76

Patients sometimes report that they have the following symptoms or problems. Please indicate the extent to which you have experienced these symptoms or problems during the past week. Please answer by circling the number that best applies to you.

During the past week:

	Not at all	A little	Quite a bit	Very much
55. Have you had swelling in one or both legs?	1	2	3	4
56. Have you felt heaviness in one or both legs?	1	2	3	4
57. Has the skin felt tight in your leg(s)?	1	2	3	4
58. Have you had pain in your leg(s)?	1	2	3	4
59. Have you had swelling in the genital area?	1	2	3	4
60. Has the skin felt tight in your genital area?	1	2	3	4
61. Have you had swelling in your groin?	1	2	3	4
62. Have you had sore skin in your groin?	1	2	3	4
63. Have you had pain in your groin?	1	2	3	4

© Copyright 2020 EORTC Quality of Life Group. All rights reserved.

LYMQOL LEG- Scoring System
Lymphoedema Quality of Life Tool

The score for the individual responses are given below. If the item is not scored and left blank or not applicable this is scored with a 0. Domain totals are calculated by adding the individual scores and dividing the total by the number of questions answered. (If >50% of questions per domain are not answered this cannot be calculated and =0).
 The four domains and their corresponding questions are: Function 1 (a-f), 2,3
 Appearance 4,5,6,7,8,9,10 Symptoms 11,12,13,14,15 and Emotion 16,17,18,19,20,21.
 Overall quality of life (Q22) is scored as the value marked by the patient, between 0-10.

(Q1) How much does your swollen leg affect the following activities?

If any of the items are not applicable to you, please write N/A in the relevant answer box(es)

- a) your walking
- b) your ability to bend, e.g. to tie shoelaces or cut toenails
- c) your ability to stand.
- d) your ability to get up from a chair.
- e) your occupation
- f) your ability to do housework

Not at all	A little	Quite a bit	A lot
1	2	3	4
1	2	3	4
1	2	3	4
1	2	3	4
1	2	3	4
1	2	3	4

(Q2) Does the swelling affect your leisure activities/ social life?

1	2	3	4
---	---	---	---

Please give examples of this

.....

(Q3) How much do you have to depend on other people?

1	2	3	4
---	---	---	---

(Q4) How much do you feel the swelling affects your appearance?

(Q5) How much difficulty do you have finding clothes to fit?

(Q6) How much difficulty do you have finding clothes you would like to wear?

(Q7) Do you have difficulty finding shoes to fit?

(Q8) Do you have difficulty finding socks/ tights/ stockings to fit?

(Q9) Does the swelling affect how you feel about yourself?

(Q10) Does it affect your relationships with other people?

Not at all	A little	Quite a bit	A lot
1	2	3	4
1	2	3	4
1	2	3	4
1	2	3	4
1	2	3	4
1	2	3	4

Not at all	A little	Quite a bit	A lot
1	2	3	4
1	2	3	4
1	2	3	4
1	2	3	4
1	2	3	4

(Q11) Does your lymphoedema cause you pain?

(Q12) Do you have any numbness in your swollen leg(s)?

(Q13) Do you have any feelings of "pins & needles" or tingling in your swollen leg(s)

(Q14) Does (do) your swollen leg(s) feel weak?

(Q15) Does (do) your swollen leg(s) feel heavy?

In the past week....

(Q16) Have you had trouble sleeping?

(Q17) Have you had difficulty concentrating on things, e.g. reading?

(Q18) Have you felt tense?

(Q19) Have you felt worried?

(Q20) Have you felt irritable?

(Q21) Have you felt depressed?

(Q22) Overall, how would you rate your quality of life at present?
Please mark your score on the following scale:

Please mark your score on the following scale:

0 1 2 3 4 5 6 7 8 9 10
poor excellent

Thank you for completing this form.

If you have any comments or queries about it, please discuss these with

Dr [name], Consultant

Questions 16 to 21 have been reproduced with permission from the EORTC. These questions are only a part of the QLQ-C30 Questionnaire.

Copyright November 2007 Ref LEG VII

All rights reserved. This document can be used or reproduced freely. If all or part of the documents be reproduced, we request that the source and copyright owners be acknowledged. Application for the copyright owners permission should be forwarded in writing to [name], Consultant in Palliative Medicine, Nightingale Macmillan Unit, [name].

EORTC QLQ-C30 (version 3)

We are interested in some things about you and your health. Please answer all of the questions yourself by circling the number that best applies to you. There are no "right" or "wrong" answers. The information that you provide will remain strictly confidential.

Please fill in your initials:

Your birthdate (Day, Month, Year):

Today's date (Day, Month, Year):

31

1. Do you have any trouble doing strenuous activities, like carrying a heavy shopping bag or a suitcase?
2. Do you have any trouble taking a long walk?
3. Do you have any trouble taking a short walk outside of the house?
4. Do you need to stay in bed or a chair during the day?
5. Do you need help with eating, dressing, washing yourself or using the toilet?

	Not at All	A Little	Quite a Bit	Very Much
1	1	2	3	4
2	1	2	3	4
3	1	2	3	4
4	1	2	3	4
5	1	2	3	4

During the past week:

6. Were you limited in doing either your work or other daily activities?
7. Were you limited in pursuing your hobbies or other leisure time activities?
8. Were you short of breath?
9. Have you had pain?
10. Did you need to rest?
11. Have you had trouble sleeping?
12. Have you felt weak?
13. Have you lacked appetite?
14. Have you felt nauseated?
15. Have you vomited?
16. Have you been constipated?

	Not at All	A Little	Quite a Bit	Very Much
6	1	2	3	4
7	1	2	3	4
8	1	2	3	4
9	1	2	3	4
10	1	2	3	4
11	1	2	3	4
12	1	2	3	4
13	1	2	3	4
14	1	2	3	4
15	1	2	3	4
16	1	2	3	4

Please go on to the next page

During the past week:

During the past week:	Not at All	A Little	Quite a Bit	Very Much
17. Have you had diarrhea?	1	2	3	4
18. Were you tired?	1	2	3	4
19. Did pain interfere with your daily activities?	1	2	3	4
20. Have you had difficulty in concentrating on things, like reading a newspaper or watching television?	1	2	3	4
21. Did you feel tense?	1	2	3	4
22. Did you worry?	1	2	3	4
23. Did you feel irritable?	1	2	3	4
24. Did you feel depressed?	1	2	3	4
25. Have you had difficulty remembering things?	1	2	3	4
26. Has your physical condition or medical treatment interfered with your family life?	1	2	3	4
27. Has your physical condition or medical treatment interfered with your social activities?	1	2	3	4
28. Has your physical condition or medical treatment caused you financial difficulties?	1	2	3	4

For the following questions please circle the number between 1 and 7 that best applies to you

29. How would you rate your overall health during the past week?

1 2 3 4 5 6 7

Very poor

Excellent

30. How would you rate your overall quality of life during the past week?

1

— 55 —

EORTC QLQ – CX24

Patients sometimes report that they have the following symptoms or problems. Please indicate the extent to which you have experienced these symptoms or problems, please answer by circling the number that best applies to you.

During the past week:

	Not at all	A little	Quite a bit	Very much
31. Have you had cramps in your abdomen?	1	2	3	4
32. Have you had difficulty in controlling your bowels?	1	2	3	4
33. Have you had blood in your stools (motions)?	1	2	3	4
34. Did you pass water/urine frequently?	1	2	3	4
35. Have you had pain or a burning feeling when passing water/urinating?	1	2	3	4
36. Have you had leaking of urine?	1	2	3	4
37. Have you had difficulty emptying your bladder?	1	2	3	4
38. Have you had swelling in one or both legs?	1	2	3	4
39. Have you had pain in your lower back?	1	2	3	4
40. Have you had tingling or numbness in your hands or feet?	1	2	3	4
41. Have you had irritation or soreness in your vagina or vulva?	1	2	3	4
42. Have you had discharge from your vagina?	1	2	3	4
43. Have you had abnormal bleeding from your vagina?	1	2	3	4
44. Have you had hot flushes and/or sweats?	1	2	3	4
45. Have you felt physically less attractive as a result of your disease or treatment?	1	2	3	4
46. Have you felt less feminine as a result of your disease or treatment?	1	2	3	4
47. Have you felt dissatisfied with your body?	1	2	3	4

Please go on to the next page

During the past 4 weeks:

	Not at all	A little	Quite a bit	Very much
48. Have you worried that sex would be painful?	1	2	3	4
49. Have you been sexually active?	1	2	3	4

**Answer these questions only if you have been
sexually active during the past 4 weeks:**

	Not at all	A little	Quite a bit	Very much
50. Has your vagina felt dry during sexual activity?	1	2	3	4
51. Has your vagina felt short?	1	2	3	4
52. Has your vagina felt tight?	1	2	3	4
53. Have you had pain during sexual intercourse or other sexual activity?	1	2	3	4
54. Was sexual activity enjoyable for you?	1	2	3	4

© QLQ-CX24 Copyright 2003 EORTC Quality of life Group. All rights reserved.

EORTC QLQ – EN24

Patients sometimes report that they have the following symptoms or problems. Please indicate the extent to which you have experienced these symptoms or problems.

During the past week:

	Not at all	A little	Quite a bit	Very much
31. Have you had swelling in one or both legs?	1	2	3	4
32. Have you felt heaviness in one or both legs?	1	2	3	4
33. Have you had pain in your lower back and / or pelvis?	1	2	3	4
34. When you felt the urge to pass urine, did you have to hurry to get to the toilet?	1	2	3	4
35. Have you passed urine frequently?	1	2	3	4
36. Have you had leaking of urine?	1	2	3	4
37. Have you had pain or a burning feeling when passing urine?	1	2	3	4
38. When you felt the urge to move your bowels, did you have to hurry to get to the toilet?	1	2	3	4
39. Have you had any leakage of stools?	1	2	3	4
40. Have you been troubled by passing wind?	1	2	3	4
41. Have you had cramps in your abdomen?	1	2	3	4
42. Have you had a bloated feeling in your abdomen?	1	2	3	4
43. Have you had tingling or numbness in your hands or feet?	1	2	3	4
44. Have you had aches or pains in your muscles or joints?	1	2	3	4
45. Have you lost hair?	1	2	3	4
46. Has food and drink tasted differently from usual?	1	2	3	4

Please go on to the next page

During the past week:

	Not at all	A little	Quite a bit	Very much
47. Have you felt physically less attractive as a result of your disease or treatment?	1	2	3	4
48. Have you felt less feminine as a result of your disease or treatment?	1	2	3	4

During the past 4 weeks:

	Not at all	A little	Quite a bit	Very much
49. To what extent were you interested in sex?	1	2	3	4
50. To what extent were you sexually active?	1	2	3	4

Answer these questions only if you have been sexually active during the past 4 weeks:

	Not at all	A little	Quite a bit	Very much
51. Has your vagina felt dry during sexual activity?	1	2	3	4
52. Has your vagina felt short and / or tight?	1	2	3	4
53. Have you had pain during sexual intercourse or other sexual activity?	1	2	3	4
54. Was sexual activity enjoyable for you?	1	2	3	4
